### 8.1.2. Secondary Analyses

#### First Secondary Analysis: Off-Protocol Intervals Included with No Adjustments

In a secondary analysis of the primary outcome all available bleeding assessment data, whether collected on- or off-protocol, will be used and attributed to the randomized treatment in the spirit of an intention to treat analysis. No imputation will be carried out for bleeding status on days following drop-out as the offset deals with censoring and the resulting variation in the days at risk.

#### Second Secondary Analysis: Off-Protocol Intervals Excluded

In another secondary analysis of the primary outcome, bleeding data will be excluded during off-protocol intervals and the offset will be computed based on the number of on-protocol days which bleeding was assessed for the negative-binomial model. Subjects who obtain transfusion independence while on-protocol will be assumed to experience no further WHO grade 2 or higher bleeding and treated as if they

had bleeding assessed on each of those days. No bleeding data will be imputed following dropout if it occurs and the offset will accommodate different durations of time at risk.

### First Sensitivity Analysis: Imputing Bleeding Status for Missing Data

In the analyses discussed to this point, on-protocol days without bleeding data recorded are not counted in the total number of days at risk. An additional sensitivity analysis will be carried out using a negative binomial model for imputing bleeding status on the on-protocol days when bleeding data is missing [2]. First, off-protocol periods of time will use the simulated bleeding rate simulated for the primary analysis in Section 8.1.1. Then the imputation for missing bleeding assessment days will be carried out by fitting an auxiliary negative binomial imputation model to the available data including these covariates: age, sex, treatment arm, treatment type strata, and pre-treatment platelet count. The imputation model will be run fifty (50) times and PROC MIANALYZE will be used to adjust variance estimates for multiply imputed data.

### Second Sensitivity Analysis: Poisson Model with Robust Variance

In addition to fitting a negative binomial model to the data from completed and simulated observations, a Poisson model with robust variance estimation will be fit as a sensitivity analysis to the primary analysis.

### 8.1.3. Assessment of Non-Inferiority and Superiority

An NI analysis will be carried out to assess the primary efficacy endpoint with the null hypothesis being the MIRASOL arm is inferior to the CONTROL arm and the alternative hypothesis being the MIRASOL arm is non-inferior to the CONTROL arm. The null ( $H_0$ ) and alternative ( $H_a$ ) hypotheses are defined as:

$$H_0: \frac{\lambda_T}{\lambda_C} \geq \delta \text{ and } H_a: \frac{\lambda_T}{\lambda_C} < \delta \text{ respectively}$$

where  $\lambda_T$  is the mean rate of the MIRASOL group,  $\lambda_C$  is the mean rate of the CONTROL group, and,  $\delta$  is the NI margin. To facilitate analysis, the null and alternative hypotheses are expressed on the natural logarithmic scale and take on the following forms.

$$H_0: \ln(\lambda_T) - \ln(\lambda_C) \geq \ln(\delta) \text{ and } H_a: \ln(\lambda_T) - \ln(\lambda_C) < \ln(\delta)$$

Specifically, a 95% confidence interval (CI) will be created about the point estimate (equivalent to a one-sided CI with an alpha level of 0.025) to test the null hypothesis, where the point estimate is defined as  $\ln(\lambda_T) - \ln(\lambda_C)$ . This parameter estimate will be obtained by fitting a negative binomial regression model with a natural log link, the response being the total number of WHO  $\geq 2$  grade bleeding days, a single treatment covariate which is 1 for individuals assigned to the MIRASOL product and 0 for those assigned the CONTROL, and with an offset of the  $\ln(\text{number the number of days bleeding was assessed})$ .

If the upper bound of the 95% CI is less than  $\ln(\delta)$ , then, NI of the MIRASOL arm relative to the CONTROL arm is inferred. Conversely, if the upper bound of the 95% CI is greater than or equal to  $\ln(\delta)$ , NI is not demonstrated. In this study, the NI margin is 1.6. Justification of the value of 1.6 for the NI margin is provided in the CIP.

If NI is demonstrated, superiority of the MIRASOL arm versus the CONTROL arm will be examined. Superiority of the MIRASOL arm compared to the CONTROL arm will be demonstrated if the upper bound of the 95% CI is less than zero ( $\ln(1)=0$ ).

Results of the primary analysis will be displayed by treatment group and will include the average number of grade 2 or higher bleeds (including minimum and maximum), the average duration of on-protocol days or days of transfusion dependence (including minimum and maximum), the estimate of the mean rate, the natural logarithm of the estimate of the mean rate and the corresponding 95% CIs. The value of the point estimate, i.e.  $\ln(\lambda_T) - \ln(\lambda_C)$ , and its corresponding 95% CI will also be displayed.

An NI analysis will also be carried out to assess the secondary efficacy endpoint of proportion of subjects with  $\geq$  grade 2 bleeding (Section 8.2.2 below). We let  $p_i$  and  $p_c$  represent the probability of a patient experiencing WHO  $\geq$  grade 2 or higher bleeding in the MIR or CONTROL arm, respectively. With an NI margin of 1.2, the null hypothesis is  $H_0: p_i/p_c > 1.2$  (MIR has more than a 20% higher probability of a patient experiencing at least one WHO  $\geq$  grade 2 bleed compared to CONTROL). The alternative hypothesis is  $H_A: p_i/p_c \leq 1.2$  (MIR has no more than a 20% higher relative bleeding rate compared to CONTROL). The risk difference will be calculated using the Wald Test.

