### **6.1. Study Design**

This is a prospective, multi-center, controlled, randomized study in which a non-inferiority (NI) design will be employed to evaluate the clinical effectiveness of Mirasol (MIR)-treated versus Conventional (CONTROL) apheresis (Aph) platelets (PLTs) in subjects with hematologic malignancies with hypoproliferative thrombocytopenia expected to have PLT count(s)  $\leq 10,000/\mu\text{L}$  and requiring  $\geq 2$  PLT transfusions. Subjects will be randomized by a ratio of 1:1 (MIRASOL vs CONTROL group) using a permuted-block schedule stratified by investigational site and type of treatment (allogeneic transplant vs autologous transplant vs chemotherapy). Randomization will occur as close to the initiation of the first study transfusion as possible, within five (5) days prior to the anticipated initiation of PLT transfusion(s).

Subject participation will be for up to eighty-one 81 days; a 14-day screening period, a 28-day treatment period, and a 28-day follow-up period. Study Day (also referred to in this document as ‘Day’) 0 of the treatment period is defined as the day of the first study transfusion following randomization. The primary, secondary, and exploratory endpoints will be based on data captured during the treatment period (Day 0 to transfusion independence or Day 28, whichever comes first). Transfusion independence is defined as ten (10) days without a PLT transfusion prior to date of last contact or Day 28 whichever is earlier. The date of transfusion independence will be the 10th day without a PLT transfusion.

Daily bleeding assessments assess bleeding for the previous day. The first bleeding assessment to be used for analysis of primary and secondary endpoints etc., will be collected on Study Day 1 which assesses bleeding at Study Day 0. Bleeding assessments are planned to occur on Study Days 0-27 and at the post transfusion follow-up visit. Consequently, there will be a maximum of 28 bleeding assessment days used for analysis. The bleeding assessments to be included in analysis are greyed out the in schematic below.

Study Day	0 (first transfusion day)*	1	2	3	4	5	6	27	Post transfusion/ Follow-up (in some cases Study Day 28)
Day bleeding assessed (24 hours previous to Study Day)	-1	0	1	2	3	4	5	26	27 + 2-day window allowed for visit

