### 6.3.3. Sample Size

A total of approximately 558 mITT subjects will be randomized in a 1:1 fashion to MIRASOL:CONTROL. This sample size estimate accounts for 10% of subjects who are randomized but will never receive an on-study transfusion and thus, will not be included in the mITT analysis set and, therefore, the primary analysis. A total of 558 mITT subjects in MIRASOL versus CONTROL will provide approximately 85% power for establishing non-inferiority at the 1-tailed 0.025 level of significance (using a 2-sided 95% CI) accommodating a 10% relative increase in the mean rate of WHO grade 2 or higher bleeding (i.e.  $\mu_T / \mu_C = 1.1$ ).

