### **7.4.2. Adjustments for Covariates**

Covariate adjustment will be utilized in both supporting and subgroup analysis of the primary endpoint and is discussed in Section 8.

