### 8.1.4. Supporting Analyses

#### First Supporting Analysis: Study Site and Type of Treatment Included as Covariates

Supporting analysis will be conducted with regard to the Primary Efficacy Endpoint although no statistical inferences will be made regarding these analyses, i.e. p-values calculated will be considered descriptive only. A supporting analysis will be conducted by including the study site and type of treatment (allogeneic transplant vs autologous transplant vs chemotherapy) variables in the model. Treatment group by site and type of treatment interactions will be reported where other interaction terms may also be considered. To facilitate interpretation, exponentiated results will be provided.

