A completed dataset will then be available with the first half of the sample representing individuals for whom data are recorded and the second half of the sample representing simulated data representing contributions from individuals yet to be recruited. A negative binomial model will be fitted to this complete dataset as described for the primary analysis. A Wald-based two-sided 95% confidence interval will then be constructed for the regression coefficient of the treatment indicator based on this completed dataset. It will then be recorded whether the upper limit of this confidence interval includes the value of  $\ln 1.6$  which defines the non-inferiority margin on the scale of the natural logarithm.

Ten thousand datasets will be computed in this way and the proportion of completed datasets for which the upper limit of a two-sided 95% confidence interval is below the value of  $\ln 1.6$  will be taken as the empirical conditional power. If this empirical conditional power is below 0.30 the guidance would suggest termination for futility, but this would not be a binding rule. Factors other than the empirical conditional power will be considered when weighing the futility of the study as a whole.

The DMC will be fully unblinded in its assessment of safety and efficacy data at the time of the formal IA. The IA tables will be prepared semi-blinded by treatment codes (e.g. Treatment A and Treatment B) and the actual treatment assignments will be provided to the DMC under separate cover.

Note that the power calculation does not consider the minor power loss due to the futility analysis. The study will not be stopped at the IA for a positive primary efficacy outcome (e.g. non-inferiority or superiority of MIRASOL).

The DMC will receive their routine unblinded DMC report at the IA. In addition, the following data will be included in the IA report:

A summary of the mean, SD, minimum and maximum days of grade 2 or higher bleeding and days of bleeding assessments will be included by treatment group alone and by treatment group and treatment type.

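### Treatment type stratifies the randomization but is absent from the deciding negative binomial model; standardising over it keeps the stated null and may narrow the interval slightly

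*SAP*

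**What the plan says.** SAP 6.1 randomizes 1:1 "using a permuted-block schedule stratified by investigational site and type of treatment (allogeneic transplant vs autologous transplant vs chemotherapy"). In 8.1.3 the deciding model is negative binomial with a log link, an offset of log assessment days and "a single treatment covariate which is 1 for individuals assigned to the MIRASOL product and 0 for those assigned the CONTROL". Its upper 95% limit is compared with ln 1.6 for non-inferiority and then with 0 for superiority. The same section states the null on arm mean rates: λ_T "is the mean rate of the MIRASOL group", and λ_C is the counterpart for control.

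Section 7.4.2 limits adjustment: "Covariate adjustment will be utilized in both supporting and subgroup analysis of the primary endpoint". The supporting model in 8.1.4 adds site and type, reports their interactions with treatment, and is explicitly non-deciding: "no statistical inferences will be made regarding these analyses, i.e. p-values calculated will be considered descriptive only".

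Elsewhere the plan treats type as relevant to bleeding. It is a covariate in the imputation model of 8.1.2, and the interim summary of bleeding days (8.6) "will be included by treatment group alone and by treatment group and treatment type". On the margin, 8.1.3 says only: "Justification of the value of 1.6 for the NI margin is provided in the CIP". The CIP is not among the documents, so the sponsor's reason for the arm-only model cannot be checked.

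**The concern.** Stratified randomization balances type across arms, so differences in bleeding between types add little to the true variability of the arm comparison. A model with arm alone does not know this and counts those differences as dispersion. If type predicts bleeding, the reported standard error is then larger than the design warrants, and so is the limit on which both claims rest. Type is recorded for every subject at randomization, so using it needs no new data. What is at stake is a little precision, not the validity of the test.

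**Working it through.** **1. The plan's own figure.** SAP 6.3.3 says that 558 mITT subjects "will provide approximately 85% power for establishing non-inferiority at the 1-tailed 0.025 level of significance", at a true ratio of 1.1. The control mean and the dispersion are not given, so the 85% cannot be reproduced independently. Working backwards:

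- SE of the log ratio = ln(1.6/1.1) / (1.960 + 1.036) = 0.3747 / 2.996 = 0.125.
- With SE² = (2/279) × V, where V is the average over arms of (1/mean + dispersion), V = 0.12505² × 139.5 = 2.18. Pairs that fit are a control mean of 1 day with dispersion 1.23, 2 days with 1.70, or 4 days with 1.94.

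**2. Analyses compared.**

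- *Arm-only*: the model of 8.1.3.
- *Standardised*: a rate r_as for each arm a and type s; R_a = Σ w_s r_as, where w_s is the pooled mITT share of type s; ln(R_T/R_C) with a delta-method SE. This keeps the null of 8.1.3.
- *Main effect*: arm plus type. This estimates a common within-type ratio.

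**3. Simulation inputs.** From the documents: 558 subjects, 1:1 allocation, margin 1.6, true ratio 1.1, at most 28 days, one-sided 0.025. Assumed: three equal types, 10 sites, blocks of 4, control mean 2 days, 10% drop-out on days 3-27, and gamma-Poisson counts capped at days assessed. Within-type dispersion (1.66, 1.60, 1.41, 1.15 for the four patterns below) is set so that the arm-only SE is 0.125.

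**4. Non-inferiority power (%) at a common ratio of 1.1** (3000-7000 trials per pattern):

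| Bleeding rates by type | Arm-only | Standardised | Main effect |
|---|---|---|---|
| 1:1:1 | 84.5 | 84.6 | 84.6 |
| 0.75:1:1.25 | 85.1 | 85.1 | 85.5 |
| 0.5:1:1.5 | 85.5 | 85.8 | 87.7 |
| 0.4:1:2.0 | 84.6 | 86.4 | 90.1 |

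The SEs (arm-only / standardised / main effect) are 0.125 / 0.124 / 0.120 in the third row and 0.125 / 0.121 / 0.114 in the fourth. The standardised gain is 0 to about 1.7 points (1.8 from the rounded entries).

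Variants at 0.5:1:1.5 give standardised gains of 0.2 and 0.1 (type shares 20/30/50 and 50/30/20), and 1.5 and -0.5 (control mean 1 and 4 days). The Monte Carlo SE of these paired differences is 0.1 to 0.5 points, so several cannot be told from zero.

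Repeat runs gave, arm-only to standardised, 86.0 to 86.2 and 84.6 to 84.7 at 0.5:1:1.5, and 85.5 to 87.1 and 86.2 to 87.4 at 0.4:1:2.0. In the last of these the arm-only SE was 0.125 against an actual spread of the estimate of 0.117, which is the mechanism described above.

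**5. False non-inferiority (%) at an arm mean-rate ratio of exactly 1.6** (4000-8000 trials, Monte Carlo SE 0.2-0.4):

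| Relative effect by type, low to high risk | Arm-only | Standardised | Main effect |
|---|---|---|---|
| Same in all types | 2.0-2.4 | 2.3-2.4 | 2.2-2.5 |
| 1.0:1.1:1.2 | 2.1-2.5 | 2.4 | 3.7-3.8 |
| 0.9:1.1:1.3 | 1.7-2.5 | 2.0-2.6 | 6.3-6.8 |
| 1.3:1.1:0.9 | 2.6-2.9 | 2.8 | 1.0-1.4 |

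The standardised mean log ratio is within 0.0005 of the arm-only one in every scenario. Further checks of the standardised test gave 2.9% (dispersion differing by type), 2.6% (drop-out 10/20/40% by type with effects 0.9:1.1:1.3) and 2.4% (shares 10/30/60).

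**6. Why the main-effect ratio differs.** Take shares 0.40/0.25/0.35, control rates 4:1:2 and type ratios 1.8/1.2/1.3. The arm mean-rate ratio is (1.6×1.8 + 0.25×1.2 + 0.7×1.3) / (1.6 + 0.25 + 0.7) = 4.09/2.55 = 1.60, which is on the margin. A very large simulated data set gave 1.59 from the arm-only model and 1.48 from the main-effect model.

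**The case against.** The strongest case for leaving the plan alone is that it is consistent and its test is sound. Sections 7.4.2, 8.1.3 and 8.1.4 all make the unadjusted model primary and the adjusted one supporting, and 8.1.4 reports the treatment-by-type interaction. For the stated null the attainable gain is close to nil in most scenarios. All of that stands, and it is why this is a suggestion.

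It also stands that the size rests on assumptions. The largest gain needs a fivefold spread of rates between types (0.4 to 2.0). The simulation also omits two parts of the endpoint in 8.1.1: the zero-bleeding days credited after transfusion independence and the simulated off-protocol counts.

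Site is a stratifier too. It is left in 8.1.4 because crossing it with arm and type would create many small cells, some without bleeding days.

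Three stronger readings might be inferred, and the documents support none of them:

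- *The plan does not say which ratio is tested.* It does: 8.1.3 names the arm mean-rate ratio.
- *The arm-only test is invalid or underpowered.* Its false non-inferiority rate was 1.7 to 2.9%, and every scenario was calibrated to the SE that the stated 85% implies, so no shortfall is shown.
- *Type should go in as a main effect, for up to about 5.5 points.* That changes the hypothesis. Against the null of 8.1.3, false non-inferiority rises to 6.3-6.8% when the effect worsens with type risk. Whether 1.6 was justified for a within-type ratio cannot be seen without the CIP.

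**Conclusion.** The point holds as a small efficiency improvement. A recorded stratifier is left out of the deciding analysis, and the resulting interval is somewhat wider than necessary if, and only if, type predicts bleeding. Keeping the null of 8.1.3, the expected gain is about 0 to 2 power points under assumed type rates; one assumed variant gave -0.5, and zero is plausible. Confidence is medium, because the documents give no rates or shares by type and no dispersion. Priority is optional to modest.

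**What to change.** Before outcome data by arm are seen:

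- In 8.1.1 and 8.1.3, prespecify that the deciding analysis fits negative binomial rates by arm and type, averages each arm's rates over the pooled mITT type shares, and compares the log ratio with ln 1.6 (then with 0) using a delta-method SE. Set in advance a rule for merging a type that has no bleeding days in an arm. Report the arm-only model beside it.
- Amend 7.4.2 to match. Carry the change into the analyses that reuse the primary model: the robust Poisson analysis (8.1.2), the per-protocol and site-exclusion analyses (8.1.4) and the subgroups (8.1.5).
- In 8.1.4, add a supporting model with type as a main effect and no interactions. State that its ratio differs from that of 8.1.3 if the effect varies by type. Do not let it decide unless the null is redefined and the CIP margin justification is confirmed for a within-type ratio.
- If the interim analysis is still ahead, change 8.6 to draw each future subject's type together with observation time, and to simulate from rates by arm and type in place of one intercept-only model per arm.

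The cost is four extra parameters (six rates in place of two), a short post-estimation step, SAP wording in the sections named and, if the interim is still ahead, a small programming change. No new data are needed.

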### 6.3.1. Primary Endpoint

The primary study objective will be assessed through examination of the Primary Efficacy Endpoint where clinical effectiveness will be measured by comparing the days of grade 2 or higher bleeding over the treatment period between the MIRASOL and CONTROL groups. Specifically, this study will investigate whether MIR-treated Aph PLTs (MIRASOL) are non-inferior to conventional PLTs (CONTROL) by testing the null hypothesis that the MIRASOL arm is inferior to the CONTROL arm. The null hypothesis will be tested using a one-sided alpha level of 0.025. If NI is established, superiority of MIR-treated Aph PLTs vs Conventional PLTs will be tested using a one-sided alpha level of 0.025 by employing a closed “gate keeper” multiple testing strategy. An in-depth discussion of the analysis of the primary efficacy endpoint is provided in Section 8.1 of this document.

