### 8.1. Primary Endpoint

Bleeding assessments based on the WHO Grading Scale for Bleeding will be conducted at baseline to assess eligibility prior to randomization, as well as daily starting on Day 0 and continuing to the post-transfusion bleeding assessment OR until transfusion independence (the last day of ten [10] consecutive days without a PLT transfusion). Each bleeding assessment will document the WHO Bleeding Scale components observed over the course of the prior calendar day, from 00:00 to 23:59. As such, the analysis of the Primary Endpoint, and Secondary Endpoint #2, will be based on bleeding assessments collected on Day 1 thru Day 28 which represent bleeds which occurred on Days 0-27.

The total number of days with WHO grade 2 or higher bleeding is obtained by counting the total number of calendar days (00:00 to 23:59) on which bleeding was assessed and found to be present. For example, if a subject has WHO grade 2 bleeding on Day 1, grade 2 bleeding on Day 2, and grade 3 bleeding on Day 3, this is considered 3 days of grade 2 or higher bleeding. Hematomas (bruises), petechiae, and purpura

[figure not shown]
(e.g., types of bleeding that occur under the skin) represent unique cases in which they are only counted as additional days of bleeding if they are new or manifest in another anatomical location.

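### The model that decides non-inferiority and superiority adjusts for no baseline covariate; prespecifying those already collected could tighten the comparison with 1.6 if they predict bleeding

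*SAP*

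**What the plan says.** The CIP is not among the documents, and the file supplied as the protocol carries the same text as the SAP, so all references are to the SAP.

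- **Deciding model (8.1.3).** A negative binomial regression with a log link, an offset for days assessed, and "a single treatment covariate which is 1 for individuals assigned to the MIRASOL product and 0 for those assigned the CONTROL". The upper 95% limit is compared with ln(1.6) for non-inferiority, then with zero for superiority.
- **Policy on adjustment (7.4.2).** "Covariate adjustment will be utilized in both supporting and subgroup analysis of the primary endpoint". The deciding analysis is not mentioned.
- **Baseline bleeding (8.1).** "Bleeding assessments based on the WHO Grading Scale for Bleeding will be conducted at baseline to assess eligibility prior to randomization".
- **Imputation model (8.1.2, First Sensitivity Analysis).** Missing on-protocol days are imputed from a negative binomial model with "age, sex, treatment arm, treatment type strata, and pre-treatment platelet count".
- **Adjusted supporting model (8.1.4).** Adds site and type of treatment, which are the randomization strata in 6.1. Its p-values are descriptive.
- **Subgroup models (8.1.5).** Age and sex appear with treatment interactions.

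No planned model uses baseline grade or platelet count to adjust the treatment effect.

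**The concern.** One confidence limit decides the trial. In a negative binomial model, differences in bleeding risk between subjects that the covariates do not capture go into the dispersion parameter, and a larger dispersion widens the interval that must stay below ln(1.6). If variables measured before treatment predict bleeding days, including them shortens the interval without another subject.

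The plan collects a pre-randomization reading on the outcome scale itself, and it considers age, sex and platelet count useful enough for its imputation model. Leaving them out of the deciding model, together with the two stratification factors, may therefore forgo precision. What is at stake is the chance of demonstrating non-inferiority when it is true. The validity of the test is not in question.

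**Working it through.** **Inputs from the SAP**
- Section 6.3.1: "The null hypothesis will be tested using a one-sided alpha level of 0.025", so z = 1.960.
- Section 8.1.3: "In this study, the NI margin is 1.6".
- Section 6.3.3: "approximately 85% power for establishing non-inferiority at the 1-tailed 0.025 level of significance", "accommodating a 10% relative increase in the mean rate of WHO grade 2 or higher bleeding", so the true ratio is 1.1. I take the 558 mITT subjects as 279 analysed per arm.
- Not given: the control bleeding rate, the dispersion, and any association between a covariate and bleeding days.

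**1. The stated power.** Power = Φ(ln(1.6/1.1)/SE − 1.960). Without a rate and a dispersion, the 85% cannot be reproduced forward. Solving backward:
- SE = 0.3747/(1.960 + 1.036) = 0.1250
- With SE² = 2v/279, the variance per subject is v = 279 × 0.1250²/2 = 2.181 (using the unrounded SE)
- Largest observed ratio that passes: exp(0.4700 − 1.960 × 0.1250) = 1.252

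**2. What covariates can reduce.** v is a Poisson part plus the dispersion φ. For a control mean of μ bleeding days, the Poisson part is (1/μ + 1/(1.1μ))/2, which covariates cannot reduce. The remainder is φ. At μ = 2, for example, the Poisson part is (0.500 + 0.455)/2 = 0.477, so φ = 2.181 − 0.477 = 1.704.

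**3. Power after adjustment.** If covariates remove a share q of φ, v becomes Poisson part + φ(1 − q). At μ = 2 and q = 0.10, v = 0.477 + 1.534 = 2.011, SE = √(2 × 2.011/279) = 0.1201, and power = Φ(0.3747/0.1201 − 1.960) = 87.7%. Both μ and q are assumptions.

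| Assumed μ | Implied φ | q = 5% | q = 10% | q = 20% | q = 30% |
|---|---|---|---|---|---|
| 1 | 1.23 | 86.0% | 87.0% | 88.9% | 90.8% |
| 2 | 1.70 | 86.4% | 87.7% | 90.4% | 92.8% |
| 3 | 1.86 | 86.5% | 88.0% | 90.8% | 93.5% |
| 5 | 1.99 | 86.6% | 88.2% | 91.2% | 94.0% |

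The gain over 85% runs from 1.0 to 9.0 points.

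**4. Simulation check.** Settings: μ = 2, φ = 1.70, 279 per arm, one normally distributed covariate, counts capped at 28, 600 trials per row.

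| Covariate's own variance as a share of φ | Arm-only power | Adjusted power | Mean SE, arm-only → adjusted |
|---|---|---|---|
| 0% | 84.8% | 85.3% | 0.125 → 0.125 |
| 5% | 87.0% | 88.5% | 0.122 → 0.119 |
| 10% | 87.8% | 91.2% | 0.120 → 0.115 |
| 20% | 89.2% | 93.7% | 0.116 → 0.107 |

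Two cautions apply. The share here is not q: a covariate variance of 10% of φ leaves a residual dispersion of 2.70/1.17 − 1 = 1.31, which is about 23% below φ. The arm-only column also drifts above 85%, because the mixture is no longer exactly gamma and counts are capped, so only the within-row difference is informative. That difference is 1.5 to 4.5 points when the covariate is prognostic. When it is not, the SE is unchanged and the 0.5-point difference is within simulation error (√(0.85 × 0.15/600) = 1.5 points for a single power).

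**The case against.** The strongest reply is that nothing here is an error. Section 7.4.2 makes a deliberate choice, an arm-only model with an offset is a valid prespecified analysis, and a wider interval makes non-inferiority harder to claim. A strata-adjusted supporting analysis already exists. All of that stands, and it limits the point to efficiency.

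A reader might infer more than the documents support, in four ways:

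- **That precision is certainly lost.** Listing age, sex and platelet count in an imputation model does not show that they predict bleeding days. Baseline bleeding is an eligibility assessment, and subjects are expected to fall to very low platelet counts, so both variables may have a narrow range. The criteria are in the CIP, so this cannot be settled here.
- **That the whole variance shrinks by 1 − ρ².** With a correlation of 0.5, that shortcut gives 93.3% power. It ignores the Poisson part. Removing 25% of the dispersion gives about 90% at a mean of 1 bleeding day (v = 0.955 + 0.920 = 1.875, SE 0.1159) and about 92% at a mean of 2 (v = 0.477 + 1.278 = 1.755, SE 0.1122).
- **That platelet count plays no part in any estimate.** It informs one sensitivity estimate through the imputation model. It is only never an adjustment covariate.
- **That adjustment leaves the tested ratio unchanged without conditions.** With a log link this needs no material treatment-by-covariate interaction. The plan itself examines such interactions for age and sex (8.1.5) and for site and type of treatment (8.1.4).

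**Conclusion.** The point holds as an optional efficiency improvement. The deciding model omits every baseline covariate, including the two stratification factors, although the data for adjustment will exist. There is no bias and no type I error problem.

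The size is conditional: nil if the covariates are not prognostic, and about 1 to 9 power points if they remove 5% to 30% of the dispersion. This rests on the back-solved SE of 0.125, 279 analysed subjects per arm, and assumed means of 1 to 5 bleeding days. The documents contain nothing that selects a value within the range. The argument for acting is that the payoff is lopsided: a possible gain against almost no loss.

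**What to change.** Before unblinding:

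- **8.1.3.** Prespecify a main-effects negative binomial model with arm, type of treatment, site (with a pooling rule for small sites), baseline WHO grade, pre-treatment platelet count, age and sex, keeping the offset. Retain the arm-only model as a sensitivity analysis.
- **7.4.2.** Amend to match.
- **Baseline value.** Use the last value before randomization for these covariates. Section 7.6 takes the value closest before the first transfusion and accepts same-day values of unknown time. Because 6.1 places randomization up to five days before the anticipated start of transfusion, that value can fall after randomization.
- **Missing baselines.** State a simple imputation rule that is blind to arm.
- **Interim conditional power (8.6).** Future subjects are simulated there from intercept-only models by arm. Either keep that as a stated approximation, or resample covariates jointly with follow-up time.
- **6.3.3.** State the control rate and dispersion behind the 85%.

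The cost is SAP wording, a few degrees of freedom, the missing-baseline rule and modest programming, more if the interim simulation is rewritten. The margin of 1.6 keeps its meaning provided there is no material treatment-by-covariate interaction, and the planned interaction analyses can be used to check this.
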